The Alpert Jewish Family and Children's Service, West Palm Beach currently serves approximately 205 people who receive peer to peer support. There is not currently a waiting list so we will be recruiting people out of the community to serve as the control group. All people in both groups have access to all other services that the Jewish Family and Children's Service offers older adults in the community. People receiving peer to peer support will receive ID Numbers PB100E to PB499E and people receiving standard community services (on the wait list to receive peer to peer support) will receive ID numbers PB500C to PB999C.

A list of participants that are currently receiving peer to peer support will be uploaded into DatStat. However, only first name, age, date of birth, gender and race will be uploaded into the system. The Research Staff will keep a separate list of contact information for these participants on a secure file on her computer. Once a participant agrees to be in the study, then the additional contact information (phone number, address, last name) will be added into DatStat.

- A. One recruitment strategy will be to contact people off of a pre-specified list of people receiving peer to peer support. These people are already receiving services from the Jewish Family and Children's Service. We will send out letters to the first 10 people on the list. The letter will give them the option to call us but it will also let them know that we will be calling them within the next two weeks to see if they are interested in participating in the research study. Research staff will select the next person to call based on the number of people they are trying to recruit in each of the pre-specified categories (ex: white women 65-70). The biostatisticians have created a list of the number of people we should recruit in each demographic bucket based on the demographic breakdown of the people currently receiving peer to peer support. We will then send out the *Introductory Letter* to potential participants from the sessions (on the "wait list") and to potential participants currently receiving peer to peer support. We will send out eligibility letters to people enrolled in peer-to-peer support and to those who are eligible for peer to peer services simultaneously. Every 2-3 weeks we will send letters to 20 new people.

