Enrolling people in the study is a three step process. Step 1, is technically a pre-screen, we only want to upload people into DatStat who we think are eligible. If for whatever reason we find out that they are not eligible then we don't want them in the database. You can email [name] and she will delete their entry from DatStat. It is also a good idea for all RAs to keep a list of participants that have been deleted to ensure that you don't accidentally contact them again. Step 2 is the formal screening. If during the formal screening it turns out that they are not eligible then DatStat marks them as ineligible, and they will be removed from your workflow. They do not need to be formally exited from the study. Step 3 is when they sign the consent form during the baseline survey. Once they sign the consent form then, they are officially enrolled in the study. Moving forward, if for whatever reason the person withdraws consent, dies or meets a main study outcome that would be when you officially exit them from the study using the exit survey. The rule of thumb is we only exit people from the study who are officially enrolled, and people are only officially enrolled once they sign the consent form.

Updating or changing participant information once enrolled in study

When updating or changing participant information in Discovery, you can update participant information however you like, including assigning someone to the most accurate study group, prior to the participant signing the consent form. Once a participant signs a consent form, at that time we will consider all the information entered in Discovery to be updated and accurate. At this point some very critical variables such as study arm, race, age, gender, site, language, DOB, can never be changed, even if they are wrong. If at any time after the participant signs a

consent, you realize there is an error in one of these data categories you cannot change the information in Discovery but rather you need you to record that information in a participant log (a word document that you will keep on your computer) and you need to alert [name] of the change. Every few months [name] will ask for a copy of these participant logs. The participant log should include the Participant ID number, the person who made the change in the DatStat system, the original incorrect value and the new corrected value.

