participate in the study or would like to change your appointment time please feel free to give me a call back. My phone number is {U:RA_TELEPHONE}. Thanks and have a nice day. “

Consent and Baseline Visit

Please refer to the baseline survey documents for instructions on completing the baseline visit. Once participants sign the consent form they are officially enrolled in the study and this is considered time zero for that participant.

Monthly Postcard Reminders

We will send generic thank you and reminder postcards on the first of the month to all participants who are active in the study at months 2, 5, 8, 11. The postcard will thank them for being in the study and will remind the participant to please mark down the times they go the hospital, emergency department and urgent care on their calendars. The postcard will also include the contact information for the study staff.

Thank you for continuing to participate in the Aging in Place Study. Don't forget to mark down all the times you stay overnight in the hospital, visit the emergency room or go to urgent care on your study calendar. We look forward to talking with you very soon. (Card will have study staff phone number)

3 Month Hospital, Emergency Department, and Urgent Care Data Collection via phone

The window to complete the three month data collection on time is 2 weeks before the 3 month anniversary and 2 weeks after the 3 month anniversary. The window will close 6 weeks after the 3 month anniversary.

If we are unable to reach a potential participant, we will leave a message.

“Hi, my name is {U:RA_FIRST} {U:RA_LAST} from{U:DATSTAT:SITE}. I was calling to talk to you about the Aging in Place study. I would like to ask you a few questions for your 3 month survey so please give me a call back. If you have decided you would no longer like to participate in the study please call me with that information as well. Again this {U:RA_FIRST} {U:RA_LAST} from{U:DATSTAT:SITE}. and my phone number is{RA_TELEPHONE}. Thanks and have a nice day. “

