All medical records will be faxed to [name] in Madison, WI. Once we receive a patient's medical record we will enter the dates of hospitalizations and emergency department visits into DatStat using the Medical Record Review Form 1 and Medical Record Review Form 2. All medical records will be kept in a locked drawer in a locked office suite.

Accessing medical records for people who have died

If a participant dies prior to us accessing their medical records, we will request the legal guardian or spouse to sign a new form giving us permission to access their medical records.

Accessing medical records for people who withdraw from the study

If prior to the end of the study a participant withdraws from the study, we will ask them if it is still okay for us to access their medical records. We will remind them that they previously gave us permission to do so and that this will require no additional work on their part. If a participant agrees to this then we will follow the protocol above for accessing medical records.

Unexpected Circumstances

Some trouble shooting situations:

- If the client wants to give you food or drinks politely refuse and stress the quicker we can get the questionnaire done he/she can get back to their regular schedule.
- Participant gets tired in the middle of the questionnaire or you can tell they have lost their attention span to answer the questions. Try to complete study but if not you could try to finish questions over the phone making it easier so you don't have to go back to their homes. Payment will be sent to participant upon completion of the survey if applicable
- If there are interruptions (family comes home, friend comes by to visit, package gets dropped off, etc.) while questionnaire is being asked allow time for the participant to focus back to the task at hand.
- Canceling last minute may be an issue just be sure to make follow up phone calls to reschedule.
- Not home/forgot here the phone call the day before the scheduled time is important so they don't forget you are supposed to come over.
- For the control group a problem we may face is the fact that they don't know who the organization is and we could have higher refusals for that group.

Exiting the Study

At any time a participant has the right to exit the study. In this case you will answer the following questions on behalf of the participant and then they will not be contacted again for the purposes of the study.

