The Effectiveness of Peer-to-Peer Community Support to Promote Aging in Place

Principal Investigator: [name]

Protocol Version Date: 10/30/2017

Coordinating Center: University of Wisconsin

Co-Investigators

[name]-University of Wisconsin
[name]- Alliance for Children and Families
[name]- Alpert Jewish Family and Children's Service
[name]- Community Place
[name]- Jewish Family Service of Los Angeles

Study Coordinator: [name]

Funding Sponsor: Patient Centered Outcomes Research Network (PCORI)

Statistical Considerations

In this section, we outline in detail the strengths of our proposed sampling and analysis plan and how it is designed to address and minimize the potential limitations of our study design. Specifically, we elaborate on how we plan to make our samples in the peer-support and standard community services group comparable, despite the fact we cannot randomize all participants; how we will control for differences across sites in our analyses; and how we will deal with missing data (including loss to follow-up).

Analysis Plan The mixed experimental and quasi-experimental, matched group comparison design allows us to conduct three different analyses to accomplish both Aims 1 and 2: (1) comparing the effectiveness of peer support to standard community services at 6 months combining data from all three sites; (2) analyzing the data from AJFCS and the combined data from the other two sites to assess the internal consistency of the effectiveness across the randomized and non-randomized designs but also to assess whether the effect size is different between the two components of the study design; (3) analyzing data from AJFCS to test whether peer-support is more effective when provided for 12 months compared to 6 months. For the third analysis using AJFCS data only, we will compare 12 vs. 6 month "dose"-levels of the peer-to-peer support intervention changes in the rates of health care utilization and nursing home placement and self-rated health, wellness, depression, and anxiety of between baseline and 12 months in group randomized to get peer support relative to changes in these same measures between 6 and 12 months in the group randomized to standard community services; as reminder this group received standard services for 6 months and then transitioned into receiving peer-support between 6 and 12 months (see Figure 3).

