Randomization and matching In order to reduce potential bias further, participants from the AJFCS of Palm Beach will be allocated either to peer-to-peer support (Intervention) or standard community support (Control) in a 1:1 ratio using permuted block randomization, stratified by age, gender and race/ethnicity. Barring randomization in JFS of LA and Community Place of Greater Rochester, older adults already participating in peer-to-peer support and those on the waiting list will be matched on age, gender and race/ethnicity to mitigate potential differences between the two groups. In order to avoid reporting/ascertainment bias, calls will be made to all participating older adults and support staff at 3 and 9 months as outlined in Figure 4 above.

Sample Size Justification Given the total sample size of 720 at-risk older adults, the study has 0.80/0.85/0.90 power to detect the effect size of 0.209/0.223/0.242 for the primary outcome measure of the annualized rate of hospitalization, ED use and institutionalization at a two-tailed significance level 0.05. The effect size here is defined as the difference in the mean annualized rate of hospitalization, ED use and institutionalization between the two groups divided by the standard deviation of the annualized rate assumed to be common in the two groups. Due to random drop-out or loss to competing event of death, the study will have less power to detect the stated effect sizes or will have the stated power for larger effect sizes.

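### If AJFCS is randomised as the SAP says, the Protocol's enrolment rules leave the allocated group visible and editable until consent is signed

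*Protocol*

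**What the plan says.** The SAP (Randomization and matching) allocates AJFCS participants to peer support or standard services "in a 1:1 ratio using permuted block randomization, stratified by age, gender and race/ethnicity". Under Analysis Plan, analysis 2 sets the AJFCS result against the two non-randomised sites, and analysis 3 is described as "analyzing data from AJFCS to test whether peer-support is more effective when provided for 12 months compared to 6 months". Both treat the AJFCS arms as randomised.

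The Protocol (Updating or changing participant information once enrolled in study) gives one rule for all sites. Before consent, "you can update participant information however you like, including assigning someone to the most accurate study group". After signing, the record is taken as correct: "At this point some very critical variables such as study arm, race, age, gender, site, language, DOB, can never be changed, even if they are" in error. Later errors go into a log and the field stays as it is.

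The Protocol's own account of AJFCS contains no random allocation to arm. Its AJFCS recruitment section takes the experimental group from current recipients of peer support and the controls from community information sessions. Its Matching section lists AJFCS among the matched sites.

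**The concern.** Randomisation protects a comparison only if nobody who enrols participants can foresee or change the arm before the person is irrevocably counted. A field that staff may update until signing, followed by a freeze at signing, reverses that order: the group is open while the decision to enrol is still being made and closed only afterwards.

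At the matched sites this does no harm, because updating the group means recording correctly whether someone receives peer support. For a randomised arm there is no outside fact to correct; the arm is whatever was drawn. An AJFCS allocation placed in this workflow could be changed, or could influence who goes on to sign, before anyone counts as enrolled. Analyses 2 and 3 would then be called randomised without the safeguard that the word implies.

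**Working it through.** No figure in the plan is in dispute here, so the check sets the texts side by side.

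**1. Is the group known before consent?** Three places bear on this.
- AJFCS recruitment section: "People receiving peer to peer support will receive ID Numbers PB100E to PB499E", and controls get a separate C series. The moment of issue is not stated for AJFCS, but the series follows service status, which is known at recruitment.
- Inclusion & Exclusion Criteria: two further exclusions apply only to the peer-support group. Under Enrollment in Study, formal screening is step 2 and consent is step 3, so group must be known at screening.
- The telephone-contact section names different failed-recruitment letters for control and experimental candidates. This is weaker evidence, because the Appendix list shows the failed-contact recruitment letter for Community Place only.

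The update rule itself also presupposes a group in the record before signing. So in the only workflow described, group is visible before consent.

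**2. When does a person start to count?** Consent and Baseline Visit: "Once participants sign the consent form they are officially enrolled in the study and this is considered time zero for that participant". Anyone lost before signing is outside the enrolled set.

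**3. Where could a random draw fit?** Neither document states its timing, who holds the list, or how it is concealed. The only randomisation envelope in the Protocol chooses between two members of a household.
- Draw before consent: the arm sits in a field that staff may update, and is visible while consent is still pending.
- Draw after consent: the freeze would protect the arm. But the workflow has no step for it: the record is taken as final at signing and the arm may not be changed after that. An AJFCS exception would be needed, and none is given.

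**4. Would a problem show?** The participant log covers errors found after consent. Candidates found ineligible at pre-screen are deleted from DatStat, and keeping a list of them is only advised. Contact attempts and their outcomes are logged, so some refusals may be recoverable. No edit history for pre-consent group changes is described.

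**5. Scale.** The site goals are 226 (Community Place), 300 (AJFCS) and 60 (JFS of LA): 226 + 300 + 60 = 586, and 300/586 = 51.2%. Against the SAP's total of 720, the share is 300/720 = 41.7%. Analysis 3 uses AJFCS alone.

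The size of any bias cannot be derived. It would need the numbers reassigned, the refusals by allocated arm, and the event rates of those people; the documents give none of these. The fix changes no sample size, so the SAP's power statement is unaffected.

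**The case against.** The strongest reply is that the harm needs a sequence that no document describes. The evidence that group is visible comes from the Protocol's matched design, in which AJFCS has no random arm. The allocated arm comes from the SAP, which gives no timing. If the draw followed consent, the freeze would guard it. The reference to the most accurate group also reads as correcting a record of service status. And the underlying defect is the conflict between a matched and a randomised AJFCS.

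Much of this stands. It makes the point conditional on AJFCS being randomised, but does not remove it. Simply confirming the SAP's randomisation would leave the pre-consent rule in force and still provide no step for a later draw.

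Two stronger readings should be resisted.
- A reader might infer that staff may choose the arm at will, or that the 12- versus 6-month assignment was in fact altered or declined once known. The wording and the silence on timing do not support that. The Protocol does not describe controls moving to peer support at 6 months either.
- A reader might take the remark under Unexpected Circumstances about controls, "we could have higher refusals for that group", as refusal on learning the arm. The reason given there is that controls do not know the organisation. It supports unequal refusal between groups, not that mechanism.

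**Conclusion.** The concern holds conditionally. If AJFCS is randomised as the SAP states, the Protocol as written leaves the allocation unconcealed and editable until consent, and refusals before consent do not appear in the analysed data. Analyses 2 and 3 could not then securely be called randomised. If AJFCS is matched, as the Protocol describes, the update rule is reasonable and the fault lies in the SAP's randomised label.

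The exposed part is the AJFCS component: about half of the site goals, and all of analysis 3. The direction and size of any bias are unknown, and no percentage should be attached to it. The conclusion rests on the Protocol's workflow applying to AJFCS unchanged; a separate randomisation procedure with concealment would answer it, but neither document contains one.

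**What to change.** First reconcile the Protocol's AJFCS recruitment and Matching sections with the SAP's Randomization and matching section.

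**If AJFCS is randomised:**
- Exempt AJFCS from the pre-consent group-update rule, and keep that rule for Community Place and JFS of LA.
- Draw the arm from a concealed list after consent and the baseline survey, issue the E or C identifier only then, lock the field, and analyse by the arm drawn.
- Reconcile the two exclusions that apply only to the peer-support group, since arm would no longer be known at screening.
- For people already enrolled, tabulate pre-consent group changes and refusals by arm as far as DatStat records allow.

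**If AJFCS is not randomised, or no record of a draw exists:** report analyses 2 and 3 as non-randomised comparisons, with the corresponding adjustment and caveats.

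**Cost.** The exemption, the field lock and one table are minor. The main downside is that AJFCS participants must consent without knowing their arm, or the randomised claim is given up. If AJFCS has in practice enrolled current recipients as the experimental group, a post-consent draw would mean a different recruitment model. In that case, relabelling the analyses is the realistic course.

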Appendix	
Introductory Letter for Participants (Community Place, AJFCS, JFS of LA)	
Failed Contact Recruitment Letter (Community Place)	
Reminder Letter (Community Place, AJFCS)	
Failed Contact 3, 6, 9, 12 month data collection (Community Place)	

Recruitment Strategies

Community Place

Community Place currently has 210 people receiving peer to peer support and 408 people on the wait list to receive peer to peer support. These numbers are fluid. All people in both groups have access to all other services that community place offers older adults in their community such as access to the Senior Center, various services we can connect with through our caseworker (Home delivered meals, benefits eligibility, Catholic Family Center-Elder one, Food link, Clothing services, legal consulting services, and Life span (Financial Budgeting, caregivers plan, HEP, High Cap-Health Insurance, Elder abuse prevention, and Rep pay program)).

All the people that are in the correct age range (≥ 65 years old) and have no known cognitive impairment will be uploaded into the study database in DatStat. People receiving peer to peer support will receive ID Numbers R100E to R499E and people receiving standard community services (on the wait list to receive peer to peer support) will receive ID numbers R500C to R999C. The following variables or a subset of these variables will be uploaded for all participants: ID, First Name, Last Name, Mailing Address, Phone, Age, Date of birth, gender, race, language preference, P2P program type, peer companion name, study group, RA first name, RA last name, RA telephone, RA email, Site PI.

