- B. We are also going to hold informational sessions for the purpose of recruiting eligible participants for the study creating our "waitlist". These sessions will be held in three adult gated communities – Century Village, Golden Lakes and Banyan Springs and also our sister agencies. We will then send out the *Introductory Letter* to potential participants from the sessions (on the "wait list"). Alternatively, we will collect demographic information from participants at the information sessions and if it is feasible we may even conduct screenings on site.

We will send out eligibility letters to people enrolled in peer-to-peer support and to those who are eligible for peer to peer services simultaneously. Every 2-3 weeks we will send letters to 20 new people.

Recruitment Goal: As of September 3, 2015 the new recruitment goal at Jewish Family Services of Palm Beach will be to recruit 300 participants into the study (150 experimental and 150 control)

Jewish Family Service of LA

Jewish Family Service of Los Angeles (JFSLA) currently has 57 people receiving peer to peer support and 35 people on the wait list to receive peer to peer support. They are actively expanding their program. All people in both groups have access to all other services that JFSLA offers older adults in their community such as case management, mental health services, link to community resources, meals, and transportation.

A list of participants receiving peer to peer support will be uploaded into DatStat

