- A. One recruitment strategy will be to contact people off of a pre-specified list of people receiving peer to peer support or on the wait list to receive peer to peer support. These people are already receiving community services from JFS of LA. We will send out letters to the first 10 people on the list. The letter will give them the option to call us but it will also let them know that we will be calling them within the next two weeks to see if they are interested in participating in the research study. Research staff will select the next person to call and recruit to the study in the recruitment pattern according to the matching strategy that the biostatisticians prepared based on the sociodemographic breakdown of the clientele that are currently receiving peer to peer support. We will send out the *Introductory Letter* to potential participants on the wait list and to potential participants currently receiving peer to peer support. We will send out eligibility letters to people enrolled in peer-to-peer support and on the wait list simultaneously. Every 2-3 weeks we will send letters to 10 new people.
- B. A second recruitment strategy will be to recruit from Park LaBrea and/or meal programs that are put on by JFS of LA.

Recruitment Goal: As of February 23, 2016 the new recruitment goal at Jewish Family Services of Los Angeles will be to recruit 60 participants into the study (30 experimental and 30 control).

Contacting Potential Participants via the Telephone Prior to Enrollment in the Study (If we are unable to reach a potential participant via telephone, we will leave the following message.)

Hello {U:DATSTAT_FIRSTNAME}. My name is {U:RA_FIRST} {U:RA_LAST} from {U:DATSTAT_SITE}. I am calling to see if you would like to participate in a survey research study to better understand what helps older adults stay in their homes and communities. If you are interested in learning more about the Aging in Place study please call me back at {U:RA_TELEPHONE} and leave me a message if I'm not at my desk. Otherwise, I will call you back in one week to talk with you. If you are not interested in receiving any more calls from me about this study, please call me and let me know and I will not contact you again. Again, my name is {U:RA_FIRST} and my phone number is {U:RA_TELEPHONE} and I look forward to talking with you soon. Have a great day.

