For Community Place and Alpert Jewish Family and Children's Service (AJFCS), we are matching participants on the following characteristics: age group (<70, 70-80, and ≥ 80 years), gender (male and female), race/ethnicity (African American, Hispanic, and non-Hispanic White) and at Community Place we are also matching based on County (Monroe or Livingston).

At both all sites we are going to recruit people from the waiting list and match them with people already receiving peer to peer services. Every month research staff at UW will ask to see the matching spreadsheet as a way to monitor how matching is progressing at each site.

Enrolling more than one person per household (added 1/14/2016)

As of February 22, 2016, we will only enroll one person per household. This is the protocol for determining which person from the household we will enroll.

- a. If Participant A is enrolled in the study (signed the consent form) and they say they would like their partner would like to participate, the research staff person will let them know that according to study protocol we are only allowed to enroll one person per household. Participant A will be the person that is enrolled in the study.
- b. If prior to enrollment a study staff person is informed that both partners in a couple want to participate in the study. The staff person will let the two participants know that we can only enroll one participant from the couple. If we only need one person then the research staff will screen and enroll that person.
- c. If we know in advance there is a couple interested in participating and both people are needed for the study then we will randomly select one person per household. In this case you should screen both participants. If both participants are deemed eligible to participate you should first assign one participant heads and one participant tails. Then you should pull out the randomization envelope and open it. This envelope will tell you which participant you will enroll. At this time you will discard the envelope.

Enrollment in Study

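### At Community Place and JFS of LA the peer group comes mainly from people already on peer support, yet follow-up starts at consent and prior time on support is neither specified nor used, so the matched-site comparison is largely of continuing support

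*Protocol*

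**What the plan says.** **Who enters the peer group.** For JFS of LA and Community Place, the SAP (Randomization and matching) matches "older adults already participating in peer-to-peer support and those on the waiting list" on age, gender and race/ethnicity. The Protocol agrees. Its Matching section plans to "recruit people from the waiting list and match them with people already receiving peer to peer services", and strategy A at each of these sites is to "contact people off of a pre-specified list of people receiving peer to peer support" or on the wait list. The Protocol's counts are "Community Place currently has 210 people receiving peer to peer support", and JFS of LA "currently has 57 people receiving peer to peer support and 35 people on the wait list".

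**Possible recent starters.** Of JFS of LA the Protocol says "They are actively expanding their program". Community Place also plans a partnership to bring in more peers (Recruitment Strategies, item D).

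**When follow-up starts.** Under Consent and Baseline Visit: "Once participants sign the consent form they are officially enrolled in the study and this is considered time zero for that participant".

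**How the data are used.** Analysis 1 in the SAP's Analysis Plan is "comparing the effectiveness of peer support to standard community services at 6 months combining data from all three sites". The primary tests are two-sample tests. Later regressions adjust for stratification factors, a site indicator and other confounders that are not named. Analysis 2 sets AJFCS against the other two sites, and subgroup results by site are planned. Analysis 3 treats 12 against 6 months of support as dose levels, at AJFCS only.

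**What is not specified.** Neither document gives a support start date, a prior duration or a limit on earlier exposure. The variables listed for upload at Community Place include programme type and companion name but no start date.

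**The concern.** A person who has been on support for some time before consent is a different comparator from a person who starts at baseline. Those who began support and then stopped, moved to a higher level of care or died before consent cannot appear in the matched-site peer group. The waiting list loses people before consent too, but selection on having remained on support is specific to peers. Benefit already reached before consent is also missed, because follow-up begins after it.

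Baseline self-rated health, depression and anxiety in these peers are on-treatment values. That matters wherever such measures are analysed as change or adjusted for baseline.

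The planned handling does not reach this. Matching is demographic, plus county at Community Place. The primary tests are unadjusted. The later regressions do not name duration and cannot restore people who left support before consent.

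What is at stake is the meaning of the main result. Under the SAP, AJFCS estimates the effect of starting support, while the matched sites estimate mainly the effect of staying on it. Analysis 1 reports the two as one effectiveness result at 6 months. The SAP's own analysis 3 accepts that time on support may change the effect.

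**Working it through.** **Inputs.** Recruitment goals (Protocol, Recruitment Strategies), peers + controls: Community Place 113 + 113, AJFCS 150 + 150, JFS of LA 30 + 30. Current recipients listed: 210 and 57. SAP total 720, two-sided 0.05. All detectable effects below use 80% power, a normal approximation and a common SD, with no allowance for drop-out or matching; z = 1.960 + 0.842 = 2.802.

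**1. The plan's own figure.** 2.802 × √(4/720) = 0.209 SD, as the SAP states.

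**2. Share of the peer group affected.**
- Peer places: 113 + 150 + 30 = 293.
- At the matched sites: 113 + 30 = 143.
- 143/293 = 48.8%, a maximum.

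The share of recent starters is not in the documents, so a range is assumed:

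| Recent starters among 143 (assumed) | Longer-term recipients left | Share of 293 |
|---|---|---|
| 10% (14) | 129 | 44.0% |
| 25% (36) | 107 | 36.5% |
| 50% (72) | 71 | 24.2% |

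**3. Could current recipients fill every place?** 210 + 57 = 267 are listed, and 143/267 = 53.6%. About 54% of everyone listed would have to be eligible and consent.

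**4. What analysis 2 can detect.**
- SE of the difference between components = √(2/150 + 2/143) = 0.1653 SD; 2.802 × 0.1653 = 0.463 SD.
- The goals sum to 226 + 300 + 60 = 586. Scaled to 720 in the same split, SE = 0.1653 × √(586/720) = 0.1491, giving 0.418 SD.

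**5. What the proposed analyses can detect.** Recent starters (n) against 143 matched-site controls, 2.802 × √(1/n + 1/143):
- n = 14: 0.785 SD
- n = 36: 0.522 SD
- n = 72: 0.405 SD

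Splitting the 143 peers by prior duration (71 against 72): 2.802 × √(1/71 + 1/72) = 0.469 SD.

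**The case against.** **The design is disclosed and partly handled.** The SAP says openly that these peers are already participating and calls the design part quasi-experimental. It gives separate matched-site results through analysis 2 and the by-site subgroups, and adds adjusted regressions. This stands as credit. None of it takes account of time already on support or describes the matched-site result as continuing support.

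**Consent is a sound time zero.** A reader might infer that the time-zero rule is the error. It is not: it aligns eligibility and follow-up, and the core eligibility criteria apply to both groups at screening. The difficulty lies in who is on the peer list when consent is sought.

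**The primary test does not use baseline.** A reader might infer that on-treatment baselines distort the primary analysis. The primary outcome is an annualized rate compared by two-sample tests with no stated baseline term, so that inference fails. Baseline matters for change or baseline-adjusted analyses of health, depression and anxiety.

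**The remedy is no more precise than the existing checks.** This is correct. The duration split detects 0.47 SD against 0.46 SD for analysis 2. With two near-equal halves, any comparison of effects needs roughly twice the detectable main effect, so the low power of analysis 2 is not evidence of this defect. It is only a reason not to read a non-significant result as agreement. The effect-by-duration analysis should accordingly be exploratory.

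**Start dates may already be collected.** The baseline survey was not supplied, so this may be so. What can be said is that the Protocol and SAP neither specify nor use them.

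**Conclusion.** The point holds. At the two matched sites the comparison is largely of continuing support among people who remained in the programme versus standard services. Analysis 1 merges it with a different comparison at AJFCS. At most 143 of 293 peer places (48.8%) are affected, falling to 24.2% if half of the 143 were recent starters (assumed).

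Three stronger readings are not supported:
- That the matched-site peers are all long-term recipients. JFS of LA is expanding and Community Place seeks additional peers, so some may have started recently.
- That 143 will in fact be current recipients. That needs about 54% of those listed to be eligible and consent.
- That the bias favours peer support. Selection of people who stayed and benefit reached before consent can act in opposite directions, so neither direction nor size can be derived from the documents.

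The contrast with AJFCS assumes that the SAP governs there. The Protocol's AJFCS recruitment text and its Matching section describe recruiting current recipients at that site too. If that text governs, the issue reaches all three sites and the 48.8% no longer applies.

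This should be changed, but it does not invalidate the trial. Confidence is medium, mainly because the baseline survey was not available.

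**What to change.** 1. Obtain each matched-site peer participant's support start date from agency files, unless the baseline survey already records it.
2. Pre-specify a sensitivity analysis of the Aim 1 and Aim 2 comparisons at the matched sites limited to recent starters. Set the window from the start dates alone, before outcomes are examined. Describe prior duration in the peer group, and treat any effect-by-duration analysis as exploratory.
3. Wherever the matched-site result is reported, label it as mainly continuing support among current recipients versus standard services, and show it beside the pooled result.
4. Report analysis 2 as a difference with its confidence interval, not as a test of consistency.
5. Reconcile the Protocol's recruitment of current recipients at AJFCS with the SAP's randomization there.

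**Cost.** Up to 143 dates, and SAP wording; no redesign. The recent-starter analysis will be imprecise (detectable effect 0.78, 0.52 or 0.40 SD if 10%, 25% or 50% are recent starters, assumed) and may prove infeasible. Items 3 and 4 are worth making even then.
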